7.2 Informed Consent Process

Informed Consent is a legally effective, documented confirmation of a subject's voluntary agreement to participate in a clinical investigation after information has been given to the subject on all aspects of the clinical investigation that are relevant to the subject's decision to participate. The CIP and ICF will be approved by an IRB prior to the commencement of the clinical investigation at an investigative site. Any changes to the ICF must be approved by the IRB reviewing the application before being used to consent a prospective study subject. It is recommended, but not required, that changes made to the ICF be submitted to Tornier for review prior to being used to consent a prospective study subject. The current IRB approved version of the ICF must be used. Subjects must provide informed consent prior to any study-related procedures.

The process of obtaining a patient's informed consent will:

- Ensure that the PI or his/her authorized designee conducts the informed consent process
- Include all aspects of the clinical investigation that are relevant to the subject's decision to participate throughout the clinical investigation
- Provide opportunity for subject to ask questions
- Avoid any coercion or undue improper influence on, or inducement of, the subject to participate
- Not waive or appear to waive subject's legal rights
- Use native language that is non-technical and understandable to the subject
- Provide ample time for the subject to consider participation
- Provide the subject with a copy of the ICF
- Ensure important new information is provided to new and existing subjects throughout the clinical study
- Ensure female subjects of child bearing age understand that the risk of harm to the fetus is unknown.

The original signed and dated ICF must be retained at the investigative site and available for monitoring and auditing. A copy of the signed and dated ICF (and data privacy language where required by law) must be provided to the subject (or person who signed the form in the case of a legally authorized representative). Data protection authorization/or other privacy language needs to be collected where required by law or local regulation. If using an electronic ICF, there needs to be a documented electronic signature process which is in compliance with applicable regulations (see 21 CRF part 11). It is recommended that the informed consent process is documented in the subject's medical records. Any new information should be provided to the subject if it could affect the subject's willingness to participate.

7.3 Description of Study Procedures

Subject Questionnaire

The subject will complete a questionnaire that has questions about quality of life, daily activities, pain and satisfaction with the shoulder. The answers to the questions are used to calculate the Constant score, Age Adjusted Constant Score, ASES, SANE, EQ5D, and subject satisfaction scores. The questionnaire is in a paper format and will include brief instructions. Site personnel who will administer the questionnaire will explain the instructions to the subject. If a subject does not speak English, the questionnaire will either be translated, or read to the patient in a language he or she can understand. Subjects must complete the questionnaire on their own unless they are unable to read or write. In the case where the subject is unable to complete the questionnaire on their own, the site personnel may read the questions and answers to the subject and document their verbal response. If this occurs, it must be documented in the subject's medical records.

The Constant score, Adjusted Constant Score, ASES, SANE, Subject Satisfaction, EQ5D, and FCI assessments are described below:

- Constant score: In this score, 35 points are allocated for subjective assessments of pain and activities of daily living and 65 points are available for objective measures of range of movement and shoulder strength. A young healthy patient can therefore have a maximum score of 100 points [2].
- Adjusted Constant Score: The strength of each subject's normal shoulder may differ because of gender and age differences. The aforementioned Constant score calculation will be adjusted using normative values for the Constant score based on age and gender.
- ASES: The original American Shoulder and Elbow Surgeons Score consists of 2 portions; a medical professional assessment section and a patient self-report section. The patient self-report section, utilized in this study, is a condition specific scale intended to measure functional limitations and pain of the shoulder. The assessment takes approximately 5 minutes to complete and consists of 2 dimensions: pain and activities of daily living. The pain score is calculated from the single pain question and the function score from the sum of the 10 questions addressing function. The pain score and function composite score are weighted equally (50 points each) and combined for a total score out of a possible 100 points [1].
- SANE: The Single Assessment Numeric Evaluation rating is determined by the subject's written response to the following question "How would you rate your shoulder today as a percentage of normal (0% to 100% scale) with 100% being normal [18].
- EQ-5D: a standardized instrument for use as a measure of health outcome. It is cognitively simple, takes only a few minutes to complete, and provides a simple descriptive profile as well as a single index value for health status.
- Subject Satisfaction: Subject satisfaction will be measured by asking each subject a single subjective question. Subjects will be asked "How satisfied are you with your shoulder?" Response options include: "very satisfied, satisfied, dissatisfied, and very dissatisfied".
- FCI (Baseline ONLY): Physical function, health status, and perceived quality of life are important indicators, from the patient's perspective, of the success of medical and surgical

interventions. As a result, condition-specific and generic measures of health are used ubiquitously to evaluate medical and surgical interventions. However, in many types of research it is essential to adjust for other diseases, called comorbid diseases, in addition to the disease of concern, which may be related to the outcome(s) of interest. This is of particular importance in research conducted in older populations where many chronic illnesses may be present in the same patient. The Functional Comorbidity Index is a self-administered, general population index of comorbid diseases with physical function as the outcome of interest. The underlying premise is that diagnoses associated with physical function would be, at least in part, different from those associated with mortality, and therefore, an index designed with physical function as the outcome would perform better than indices designed with mortality as the outcome of interest. The FCI contains 18 diagnoses scored by adding the number of "yes" answers, with a score of 0, indicating no comorbid illness, and a score of 18, indicating the highest number of comorbid illnesses. [4]

Instability Tests [19]

- Sulcus sign: With the arm straight and relaxed to the side of the subject, the elbow is grasped and traction is applied in an inferior direction. With excessive inferior translation, a depression occurs just below the acromion. The appearance of this sulcus is a positive sign.
- Anterior Drawer Test: With the subject supine and the shoulder just over the edge of the table, the examiner abducts the subject's arm 60-70° with a slight internal rotation. A slight axial load is applied to the arm, the humeral head is translated anteriorly over the glenoid rim, and then the degree of anterior translation determined.
- Posterior Drawer Test: With the subject supine and the shoulder just over the edge of the table, the examiner abducts the arm 50°-60° and in neutral rotation. The examiners hand is placed with the thumb on the anterior humeral head and the remaining fingers behind the humeral head. As the thumb pushes the humeral head posteriorly, the arm is flexed forward toward the examiner. The fingers placed posteriorly can be used to feel the humeral head subluxate over the posterior glenoid rim and then the degree of posterior translation determined.

Range of Motion

Range of Motion (ROM) is a movement test conducted on a joint to diagnose level of pain and function. The shoulder joint has a greater Range of Motion than all other joints in the body, and therefore it is important that accurate measurements be obtained to diagnose shoulder health and dysfunction.

There are various methods to measuring active and passive Range of Motion in the shoulder; visual estimation, goniometry, and still photography (among other less common methods). Each of these methods has been shown to offer fair-good levels of accuracy of measurement by an experienced clinician or trained measurer. In this study, ROM will be measured using a goniometer for forward flexion in relation to the thorax, abduction, and external rotation (arm at side and arm abducted to 90°) [20]. In addition, internal rotation will be measured using anatomical landmarks [2].

Strength

The subject's strength will be assessed using a fixed force gauge. The fixed force gauge is held in place by the examiner and the subject pulls upward with maximum effort for approximately five seconds. The test can be completed up to three times and the maximum score is used, however all three pulls will be recorded. The test is done only on the affected arm. The result of this test contributes to the adjusted Constant score calculation [2] [3]. The strength test is further described in Appendix 2.

X-Ray

At least two x-ray views of the shoulder must be taken. Required views include the external rotation Grashey and axillary. Exceptions will be allowed at the immediate post-op follow-up visit if reasonable and necessary.

X-rays will be submitted to centralized independent reviewers for analysis. Two independent reviewers will analyze each x-ray and a third reviewer will adjudicate discrepancies. The reviews will be recorded electronically in the study database.

Baseline x-rays will be assessed for acromiohumeral distance, glenohumeral joint space width, glenoid osteophytes, glenoid morphology, and glenoid erosion. Follow-up x-rays will be assessed for the same things as well as humeral component radiolucency, osteolysis, migration, subsidence, subluxation, integrity, anatomic fracture, and any additional observations.

Refer to the Imaging Charter for additional information.

7.4 Data Collection

The study data that will be collected at each visit is listed in Table 3. Data will be submitted to Tornier via an Electronic Data Capture (EDC) system using electronic Case Report Forms (eCRFs). Worksheets will be provided to investigative sites to aid in data collection during subject visits. Data should be entered into the database in a timely manner. Queries will be issued via the EDC system as a part of data quality assurance and monitoring.

	Baseline (Pre-op)	Day of Surgery (DOS)	Post-op Follow-up (5-21 days)	Follow-up 3M (69-111 days)	Follow-up 6M (159-201 days)	Follow-up 12M (323-407 days)	Follow-up 24M (688-772 days)	Follow-up Annual (if applicable)
Demographics,	Х							
Medical History and								
Indication								
Intraoperative Data		Х						
Subject Questionnaire	Х			Х	Х	Х	Х	Х
Range of Motion	X			X*	X*	Х	Х	Х
Strength Test	Х			X*	X*	Х	Х	Х
Pain Medications	X	Х	Х	Х	Х	Х	Х	Х
Adverse Event		Х	Х	Х	Х	Х	Х	Х
Assessment								
X-ray	Х		Х		Х	Х	Х	Х

Table 3:	Data	Collection	Overview
----------	------	------------	----------

*Optional

7.5 Subject Follow-up Schedule

Visit windows are provided to allow scheduling flexibility. Subject follow-up visits or procedures that do not occur in the windows listed in Table 4 will be considered a study deviation and require completion of a study deviation form. The day of surgery (DOS) is considered day zero. The baseline visit is preferred to occur as close as possible to the surgery and must be within 60 days prior to surgery.

Study Visit	Visit Window		
Baseline	60 days pre-op through DOS		
Post-op Follow-up	5-21 days post-op		
3 Month Follow-up	90 Days post-op ± 21 days		
6 Month Follow-up	180 Days post-op \pm 21 days		
12 Month Follow-up	365 Days post-op \pm 42 days		
24 Month Follow-up	730 Days post-op \pm 42 days		
36 Month Follow-up (if applicable)	1095 Days post-op \pm 84 days		
48 Month Follow-up (if applicable)	1460 Days post-op \pm 84 days		
60 Month Follow-up (if applicable)	1825 Days post-op \pm 84 days		
72 Month Follow-up (if applicable)	2190 Days post-op \pm 84 days		

 Table 4: Visit Windows

7.6 Required Study Visits

Study specific procedures and assessments for all subject visits must be completed by persons authorized by the principal investigator and trained by the Tornier study team.

7.6.1 Baseline Visit

Subjects need to provide informed consent prior to any study specific procedures being performed and prior to providing subject information to the study sponsor. Inclusion and exclusion criteria will be verified at the baseline visit. Some of the inclusion/exclusion criteria need additional verification at the time of surgery. The subject is enrolled once they provide consent.

The following baseline data will be collected for all subjects prior to surgery. The baseline visit must occur within 60 days prior to surgery, except for shoulder X-rays which must be performed within 90 days prior to surgery. If the timeline is exceeded, the baseline visit assessments or X-ray must be repeated.

- Informed consent
- Data privacy language where required by law
- Subject demographics, medical history, indication for arthroplasty, tobacco use
- Pain medications usage
- Instability
 - Sulcus sign
 - Anterior and Posterior drawer test
- X-ray physician will utilize the X-rays to assess the glenoid using the following criteria:
 - Morphology (Walch Classification) [21]
 - Erosion (modified Favard Classification) [22]
 - Joint Space (subjective measurement)

- X-ray independent radiologist will utilize imaging to assess X-ray data (defined in Section 7.3)
- ROM test
- Strength test
- Subject Questionnaire (FCI will only be completed at baseline)

CT Scan is recommended for the most accurate assessment of glenoid type if there is concern regarding the glenoid bone stock. CT data is not required but may be reported if collected per investigators standard of care.

MRI is recommended to confirm the integrity of the rotator cuff (cuff tear and fatty infiltration) if there is a clinical question about the cuff integrity. MRI data is not required but may be reported if collected per investigators standard of care.

7.6.2 Day of Surgery

The general surgical procedure is described in Section 4.3. It is required that an investigator or subinvestigator perform the surgical procedure. During the surgery, the investigator will be required to assess the following exclusion criteria prior to implanting the Pyrocarbon HH. A subject will not have a Pyrocarbon HH implant attempt and will be considered an intra-operative screen failure if any of the following conditions are present.

- In the opinion of the clinician, there is insufficient bone stock to support implants in the humeral metaphysis or poor bone quality.
- In the opinion of the clinician and prior to any glenoid treatments, there is insufficient bone stock or excessive deformation of the native glenoid to allow normal functioning of the glenohumeral joint.
- A rotator cuff that is not intact and cannot be reconstructed. Subjects with a massive rotator cuff tear (>5cm) must be excluded.
- Anatomy cannot be adequately replicated using current available system sizes.

If any of the aforementioned conditions are present, the implanting physician should utilize his or her standard bailout procedure. Bailout procedures may include, but are not limited to: traditional total shoulder arthroplasty, reverse shoulder arthroplasty, another hemi shoulder arthroplasty device, or no implant.

The following data associated with the surgery will be collected and reported into the study database:

- Pregnancy Test
- Intraoperative data and observations
- Adverse events
- Pain medication usage

7.6.3 Rehabilitation Guidelines

This section describes the recommended guidelines for the subject's rehabilitation program. These guidelines may be modified by the surgeon using his/her judgment taking into consideration the subject's pathology and physical condition.

1. Subjects should wear the sling every night for at least the first 6 weeks.

- 2. Subjects should push themselves up in bed or from a chair using their non-surgical arm.
- 3. Subjects should follow their program of home exercises and don't do more than prescribed, as overuse of the shoulder can be harmful.
- 4. No sports or heavy lifting for at least 4-6 months.
- 5. Investigators will let the subject know when it is safe to drive.
- 6. Investigators should provide subjects with a specific rehabilitation protocol.
 - Passive motion only for up to 4 weeks after surgery.
 - Begin passive assisted forward elevation and external rotation on the first day after surgery.
 - Place no limit to forward elevation, but limit external rotation to the side to 30 degrees.
 - At two weeks, begin internal rotation stretching. Encourage active use of the arm for activities of daily living.
 - Active assistive motion may be initiated at 3-4 weeks.
 - Active phase initiated at 6-8 weeks, limit external rotation to 45 degrees and internal rotation to L5.
 - Isometric phase may be initiated at 3 months.
 - No vigorous strengthening until 20 weeks post-op

The study specific guidelines (Appendix 3) should be provided to subjects upon hospital discharge.

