Appendix 3 Subject Rehabilitation Guidelines

You are being asked to follow specific guidelines during your post-study implant rehabilitation. Your doctor may provide you with more detailed instructions in addition to the study guidelines. The following instructions inform you when to start using passive and active motion. Passive motion is the use of an external force (e.g., other arm) to move your treated arm. DO NOT use your treated arm muscles during passive motion. Active motion is when you start using your muscles of the treated arm without assistance.

Below are general guidelines to keep in mind during your recovery.

- Wear the sling every night for at least the first 6 weeks.
- Push yourself up in bed or from a chair using your non-surgical arm.
- Follow your program of home exercises and don't do more than prescribed, as overuse of the shoulder can be harmful.
- No sports or heavy lifting for at least 4-6 months.
- Do not drive. Your doctor will let you know when it is safe to drive

After your surgery, you should limit your shoulder motion as follows

- Passive motion ONLY for up to 3 weeks.
- Limit forward elevation to 120 degree for the first 6-8 weeks. (Figure 1)
- Passive external rotation to the side should be limited to 30 degrees (Figure 2).
- At 3-4 weeks you may begin active assistive motion. During this phase you should begin using your treated shoulder muscles along with assistance (similar to the passive phase).
- At 6-8 weeks you may begin active motions without assistance. Limit external rotation to 45 degrees and internal rotation to L5. (Figure 3)
- Isometric strengthening phase may be initiated at 3 months.
- Do not begin any vigorous strengthening until 20 weeks after surgery.

[figure not shown]
[figure not shown]

Figure 1: Active assisted Forward Elevation

[figure not shown]

Figure 3: Internal Rotation

Images adapted from http://shoulderarthritis.blogspot.com/2011_03_01_archive.html

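### Section 7.6.3 sets no limit on forward elevation, but the Appendix 3 handout it tells sites to give subjects limits it to 120 degrees for 6-8 weeks

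*Protocol*

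**What the plan says.** Protocol section 4.3, step 14, says that rehabilitation will be standardized across subjects and will align with the Surgical Manual. It sends the reader to section 7.6.3 for the study-specific instructions.

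Section 7.6.3 presents recommended guidelines that the surgeon may modify for the individual subject. Its item 6 asks investigators to give each subject a specific rehabilitation protocol and lists the steps. Two consecutive steps concern elevation: "Begin passive assisted forward elevation and external rotation on the first day after surgery", followed by "Place no limit to forward elevation, but limit external rotation to the side to 30 degrees". The second carries no end date. The section closes by telling sites to hand Appendix 3 to subjects at hospital discharge, and it attaches the study-specific label to that appendix.

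Appendix 3 introduces its list with "After your surgery, you should limit your shoulder motion as follows". Its elevation item reads "Limit forward elevation to 120 degree for the first 6-8 weeks. (Figure 1", and the figure it cites is captioned "Figure 1: Active assisted Forward Elevation". The figure itself is not reproduced in the text available for this review. The next item is "Passive external rotation to the side should be limited to 30 degrees".

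**The concern.** The section that sets out the rehabilitation plan states one elevation rule and directs sites to hand out another. The movement is the same and the early weeks overlap. The surgeon and the subject can therefore leave hospital with different default instructions, in a study that says rehabilitation is standardized.

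What is at stake is the clarity of instructions that subjects take home. Section 7.6.3 itself warns against doing more than prescribed, so what is prescribed should be unambiguous.

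**Working it through.** There is no figure in the plan to reproduce. The check sets the two texts side by side and then tests whether a difference in motion type removes the conflict.

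**Comparison of the two schedules**

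| Item | Section 7.6.3 | Appendix 3 |
|---|---|---|
| Forward elevation | no limit | 120 degrees for the first 6-8 weeks |
| Passive-only period | up to 4 weeks | up to 3 weeks |
| Early external rotation | 30 degrees | 30 degrees |
| Active-assisted motion starts | 3-4 weeks | 3-4 weeks |
| Active phase starts | 6-8 weeks | 6-8 weeks |
| Limits in active phase | external 45 degrees, internal to L5 | external 45 degrees, internal to L5 |
| Isometric phase | 3 months | 3 months |
| Vigorous strengthening | not before 20 weeks | not before 20 weeks |

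The two texts otherwise correspond closely, so elevation stands out as a specific mismatch. The passive-only ceilings differ by 4 − 3 = 1 week. Both are ceilings, so that is a difference of wording only.

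**Could the handout limit apply to active-assisted motion only?** The caption points that way. Three features of the text prevent it from settling the matter.

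1. The lead-in to the handout list is general. The elevation item names no motion type in words, while the next item names passive motion explicitly.
2. The limit is worded to run from surgery to week 6-8. Active-assisted motion starts at week 3-4 in both texts ("Active assistive motion may be initiated at 3-4 weeks" in 7.6.3; "At 3-4 weeks you may begin active assistive motion" in Appendix 3). The limit period therefore splits as follows:
   - before active-assisted motion starts: 3 to 4 weeks;
   - after it starts: from 6 − 4 = 2 weeks to 8 − 3 = 5 weeks.

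   In the first part, the handout limit meets the no-limit statement in 7.6.3 directly. Section 7.6.3 also encourages active use of the arm in daily activities from two weeks, but that still leaves the opening two weeks inside the limit period.
3. If the limit is nevertheless read as active-assisted only, 7.6.3 gives no elevation limit for those later 2 to 5 weeks either. The two texts would still not match.

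**Which text is the default?** Section 4.3 locates the study-specific instructions in 7.6.3, and 7.6.3 gives that label to Appendix 3. This can be read as a chain ending at the appendix. On that reading 7.6.3 still carries a different elevation statement of its own, and nothing says that the appendix overrides it.

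**The case against.** The strongest reply is that the two statements concern different motions. In 7.6.3 the no-limit step directly follows one about passive assisted elevation. In Appendix 3 the cited figure is captioned as active-assisted. The handout limit also ends at 6-8 weeks, which is when both texts start the active phase, as an active-assisted limit would. On this view 7.6.3 merely omits a detail that the handout supplies. That reading is plausible as to intent, and the missing figure might support it. It does not change the wording, which imposes the limit from surgery onward.

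The second reply is that both texts are guidance. The surgeon may modify them, section 1 defines *should* and *recommended* as allowing justified departures, investigators are asked to give a specific protocol, and the handout expects the doctor to add detail. This stands to a point: it makes it less likely that a subject relies on the handout alone, and it means that no mandatory rule is broken. But permission to depart from a default does not identify the default, and the handout describes the doctor's instructions as additional to the study guidelines.

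The third reply is that the Surgical Manual may resolve the point. It is not among the documents, so this cannot be known here.

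It is also fair to say that no consequence for subjects or for the trial result has been shown. That limits the weight of the point but does not remove the inconsistency.

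**Conclusion.** The concern holds. One instruction conflicts: no limit in 7.6.3 against 120 degrees for the first 6-8 weeks in the handout. The conflict is direct for the first 3-4 weeks. For the remaining 2-5 weeks the two texts differ at least by omission.

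The conclusion rests on the wording as it stands. Neither the figure nor the Surgical Manual could be seen, and either might show what was intended.

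This is an error in subject-facing guidance that should be corrected. It does not bear on the sample size or the hypothesis test, and no effect on the 24-month endpoint or on site poolability is claimed.

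**What to change.** Reconcile section 7.6.3 and Appendix 3:

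- Put the same forward-elevation statement in both, with the motion type and the period it covers.
- Use the same wording for the passive-only period in both.
- State in one place which text is the study default, and make the cross-references in 4.3 and 7.6.3 agree with it.
- Check both texts against the Surgical Manual before finalizing.

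The choice of limit belongs to the sponsor's clinical lead; none is proposed here. The cost is a wording amendment to the two passages and any affected cross-reference, plus IRB re-approval of the handout. Sample size and analysis do not change.

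### Protocol 7.6.3 and the Appendix 3 discharge handout give different default rehabilitation instructions on forward elevation and on early active use of the arm

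*Protocol*

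**What the plan says.** Section 7.6.3 of the protocol is written for investigators. It describes its content as recommended, and adds: "These guidelines may be modified by the surgeon using his/her judgment". Item 6 asks investigators to give each subject a specific rehabilitation protocol, and lists its default steps. Four of them matter here, apart from the elevation line:

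- The opening stage is given as: "Passive motion only for up to 4 weeks after surgery"
- The two-week bullet then reads: "At two weeks, begin internal rotation stretching. Encourage active use of the arm for activities of daily living"
- For the assisted step, the list has: "Active assistive motion may be initiated at 3-4 weeks"
- For the unassisted step, it has: "Active phase initiated at 6-8 weeks, limit external rotation to 45 degrees and internal rotation to L5"

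On how far the arm may be raised, the same list says: "Place no limit to forward elevation, but limit external rotation to the side to 30 degrees".

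The section ends by saying that the Appendix 3 guidelines should go to subjects at hospital discharge. Appendix 3 addresses the subject directly. It gives passive-only motion for up to 3 weeks, active-assistive motion at 3-4 weeks and unassisted active motion at 6-8 weeks. On elevation it says: "Limit forward elevation to 120 degree for the first 6-8 weeks".

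Step 14 of section 4.3 ties the two together. It says that rehabilitation will be standardized and aligned with the Surgical Manual, and it refers the surgeon to 7.6.3.

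**The concern.** A surgeon who follows 7.6.3 as written would give the subject instructions that do not fit the handout the subject already holds. The mismatch concerns how far the arm may be raised and whether it may be used actively in the early weeks. There are two plain routes to the subject: the specific rehabilitation protocol that item 6 requests, and the post-op visit at 5-21 days (7.6.4), which includes day 14.

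These are patient-care instructions for a healing shoulder, and 7.6.3 itself warns that overuse can do harm. Two different defaults also undercut the standardization promised in 4.3. What is at stake is clear and consistent instruction to subjects, not the statistical analysis. The SAP does not mention rehabilitation.

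**Working it through.** No statistical figure is involved, so the check is a line-by-line comparison of the item 6 list in 7.6.3 with the motion lines in Appendix 3.

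| Topic | Protocol 7.6.3 | Appendix 3 handout | Result |
|---|---|---|---|
| Passive-only period | up to 4 weeks | up to 3 weeks | compatible |
| Forward elevation | no limit | 120 degrees, first 6-8 weeks | conflict |
| External rotation at the side | 30 degrees | 30 degrees (passive) | agree |
| Active-assistive motion | 3-4 weeks | 3-4 weeks | agree |
| Active motion, with 45 degrees and L5 limits | 6-8 weeks | 6-8 weeks | agree |
| Isometric phase | 3 months | 3 months | agree |
| Vigorous strengthening | not before 20 weeks | not before 20 weeks | agree |
| Active use for daily living | encouraged, in the two-week bullet | no such line | conflict |

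Of the handout's 7 motion lines, 5 agree with 7.6.3, 1 is compatible and 1 conflicts (5 + 1 + 1 = 7). The last row of the table stands only in 7.6.3.

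**Forward elevation.** The list in 7.6.3 starts passive elevation on the first day after surgery and then sets no limit. The handout's cap runs from surgery to week 6-8, which is day 42 to day 56 (6 × 7 and 8 × 7). The two periods overlap from the start. In that overlap, elevation beyond 120 degrees is allowed by one text and ruled out by the other.

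**Early active use.** The sentence has no time of its own. It takes two weeks from the bullet it sits in, which is listed before the 3-4 week step. On that reading it comes 3 − 2 = 1 to 4 − 2 = 2 weeks before even assisted active motion. It also falls where the list otherwise has passive motion only. That ceiling is worded as an upper limit, so a surgeon could end the passive-only stage at two weeks. Active use would then still come before the assisted step. If the sentence is read as untimed, 7.6.3 gives no start for it at all.

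**Passive-only ceiling.** Both texts set an upper limit, and both move to active-assistive motion at 3-4 weeks. A subject who stops passive-only motion at 3 weeks satisfies both, so this is not a conflict.

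**Exposure.** Two weeks is day 14, inside the 5-21 day visit window, so the two-week advice could be given at that visit.

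**The case against.** The strongest reply is that the guidelines are advisory. Section 1 defines recommended items as open to departure for valid reasons, 7.6.3 lets the surgeon modify them, and the handout tells subjects that the doctor may add detail. This stands as far as it goes: no requirement is breached. But the discretion in 7.6.3 is tied to the subject's pathology and physical condition. It covers tailoring to an individual, and does not explain two different defaults for the same ordinary subject.

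On elevation, the absence of a limit follows a bullet about passive elevation, while the handout's line points to a figure captioned for active-assisted elevation. The two might therefore address different kinds of motion. The handout's limit, however, is worded for all of the first 6-8 weeks, which include weeks when assisted motion has not yet begun. The conflict is the more natural reading, though not a certain one.

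On active use, three stronger inferences are tempting, and the documents do not support them:

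- A reader might infer that 7.6.3 starts active motion 4-6 weeks too early (6 − 2 and 8 − 2). That requires active use for daily living to mean the same as the handout's active motion. Section 7.6.3 defines neither active use nor its active phase, and light daily use may be meant.
- A reader might take "DO NOT use your treated arm muscles during passive motion" as a ban on using the arm for weeks. It follows the definition of passive motion and says how to perform it.
- A reader might count the 3 versus 4 week ceiling as a further contradiction. As shown above, the two limits are compatible.

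Finally, the Surgical Manual might settle both points. It was not available, so the documents alone cannot show which text is the intended one.

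**Conclusion.** The point holds at low severity. There are two inconsistencies between default instructions: forward elevation (no limit against 120 degrees for 6-8 weeks) and encouragement of active daily use ahead of the active-assistive and active steps. The elevation conflict rests on reading the handout's limit as it is worded. The active-use conflict rests on taking the time from the bullet in which the sentence stands. On when active-assistive and active motion begin, the handout is coherent and matches the corresponding bullets of 7.6.3.

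A reader might infer harm to subjects, or a distortion of the Constant score change or the composite success rate. The documents give no figure that links rehabilitation timing to events or outcomes, so no effect on event rates, the 24-month endpoint or the primary test is claimed.

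**What to change.** Check the Surgical Manual first. Unless it says otherwise:

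1. Replace the unlimited forward elevation in 7.6.3 with the handout's limit of 120 degrees for the first 6-8 weeks.
2. Move the sentence that encourages active daily use from the two-week bullet to the 6-8 week active-phase bullet.
3. If early light use is intended, keep it instead, with a stated start week and limits (for example, which tasks are allowed and no resisted use), worded identically in 7.6.3 and Appendix 3.

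Keep the surgeon's discretion for individual subjects. The passive-only ceilings need no change.

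The cost is a minor protocol amendment with a reissued handout. Appendix 3 is part of the protocol, so one amendment covers both. Section 6.2 requires IRB approval of the current protocol, at up to 20 sites (2.2), and 5.4 has all sites on the same version. No visits, data or analyses are added. The benefit is limited to subjects not yet past the first 6-8 weeks after surgery, so it shrinks as enrollment proceeds. If the manual does intend early light use, step 2 without step 3 would withdraw it, which is why the manual should be checked first.
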